## 10 Efficacy

The primary efficacy endpoint will be summarized for the ITT and PP populations. CCI

Tables will be presented by treatment as described in Section 7.2 and treatment period. The planned treatment will be used. This is the randomized treatment before planned dose reduction following Amendment 2. After planned dose reduction following Amendment 2, the planned treatment is the reduced dose (CCI mg) for the C1-INH HAE subjects randomized to CCI mg in Treatment Period 2. Unplanned dose reductions or dose increase to CCI mg CSL312 q4wk will not be considered for the Efficacy analysis.

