3.3 Scientific Rationale

3.3.1 Study Design Rationale

The present phase 2 study will evaluate the efficacy, safety, tolerability, and PK profile of multiple subcutaneous administrations of CSL312 across a range of doses in subjects with C1-INH HAE or FXII/PLG HAE. The study consists of a Screening Period to assess subject eligibility, a Run-in Period to assess underlying disease activity, and 2 treatment periods to assess initial and long-term (respectively) safety, tolerability, and efficacy. The data from this study will be used to select dose(s) for a potential phase 3 study.

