5.5 Dose Modification

No modification of dose is planned in Treatment Period 1.

Subjects in Treatment Period 2 at a dose of [REDACTED] mg CSL312 q4wk who experience ≥ 3 HAE attacks within an 8-week period are eligible to have their CSL312 dose increased to [REDACTED] mg CSL312 q4wk. All CSL312 dose increases will be made in eligible subjects at the discretion of the investigator in consultation with CSL. All C1-INH HAE subjects receiving the [REDACTED] mg dose will have their dose reduced to [REDACTED] mg q4wk SC at their next scheduled study visit.

6 Allocation, Dosing, and Administration

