10.3 Statistical Analyses and Methods

The data from Treatment Period 1 and Treatment Period 2 will be analyzed separately.

In addition, Treatment Period 1 and Treatment Period 2 will be analyzed together for subjects who are being continuously administered the same dose of CSL312 in both treatment periods, unless otherwise specified. For C1-INH subjects having a dose reduction from CCI mg to CCI mg in Treatment Period 2, only data until the date and time of the dose reduction will be included.

Subjects with C1-INH HAE who are treated with placebo or CCI mg, CCI mg, or CCI mg CSL312 q4wk will be analyzed separately from subjects with C1-INH HAE who are treated with CCI mg CSL312 q2wk. Subjects with FXII/PLG HAE will be analyzed separately from subjects with C1-INH HAE.

Subject disposition will be summarized using all Subjects. Demographic and subject characteristics will be summarized using the ITT and PP populations. Safety data will be summarized using the Safety population. The primary efficacy endpoint will be summarized using the ITT and PP populations. CCI [REDACTED]

[REDACTED]. Pharmacokinetic data will be summarized using the PK population. CCI [REDACTED]

Continuous variables will be described by using mean values with their respective 95% confidence intervals (CI); standard deviation; range; 25th, 50th (median), and 75th percentiles; and counts of missing and non-missing values. The geometric coefficient of variation will be expressed as a percentage for PK and CCI data. The geometric mean and its respective 90% CI will be calculated for PK and CCI data. The 90% CI for the geometric mean will be calculated by log transforming the data, calculating the lower and upper limits of the 90% CI of the mean of the log-transformed data, and subsequently back transforming the lower and upper limits. Categorical values will be described using counts and percentages.

All data will be displayed in by-subject listings. The listings will be sorted by treatment, study site, subject, time point, and item number (if applicable).

The evaluation periods for assessment of efficacy will be:

- **The Run-in Period (all subjects):** From Week 1 (Day 1) of the Run-in Period until the date / time of the first administration of investigational product in Treatment Period 1 (ie, at the Week 1 [Day 1] Visit of Treatment Period 1).

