## 4.5 Determination of the Sample Size

### Subjects with C1-INH HAE

Seven subjects assigned to each treatment (placebo, or [REDACTED] mg, or [REDACTED] mg CSL312 q4wk) are needed to reach a power of ~82% for the comparisons of [REDACTED] mg CSL312 q4wk against placebo q4wk and [REDACTED] mg CSL312 q4wk against placebo q4wk in Treatment Period 1.

This is based on the following assumptions:

- Alpha is 2.5% for each of the 2 two-sided Mann-Whitney tests of [REDACTED] mg CSL312 q4wk or [REDACTED] mg CSL312 q4wk against placebo q4wk.
- The time-normalized number of HAE attacks is 2.9 attacks per month during treatment with placebo. This number was derived from CSL study CSL830\_3001, using the lower bound of the distribution-free 95% confidence interval (CI) for the median of the first placebo treatment period.
- The time-normalized number of HAE attacks is 0.6 attacks per month during treatment with [REDACTED] mg or [REDACTED] mg CSL312 q4wk. The number was derived from CSL study CSL830\_3001, using the upper bound of the distribution-free 95% CI for the median of the combined active treatment periods.
- For the time-normalized number of HAE attacks during CSL321 treatment and placebo a Poisson distribution is assumed. The lower bound and the upper bound, respectively, of the CIs for the medians are chosen for the rate parameters.
- Randomization allocation between CSL321 treatment and placebo which are compared are equal.

[REDACTED]

[REDACTED]. The sample size of 7 subjects for this arm is not driven by an

efficacy comparison, but instead, by consistency with other treatment arms and for maintenance of the blinding of the study. No testing for efficacy of the [REDACTED] mg CSL312 dose against placebo is planned and no power calculation has been done.

An additional subject will be added to each of these 4 treatment arms to account for dropouts during Treatment Period 1, resulting in 8 subjects required in each treatment arm.

Up to 7 subjects with C1-INH HAE will be assigned to receive [REDACTED] mg CSL312 q2wk. This arm is included for informational purposes, and therefore no testing against placebo is planned and no power calculation has been done. An additional subject will be added to this arm to account for dropouts during Treatment Period 1, resulting in up to 8 subjects in this treatment arm.

Overall, a total of up to 40 subjects with C1-INH HAE will be assigned to treatment in Treatment Period 1.

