The data from Treatment Period 1 and Treatment Period 2 will be analyzed separately. For subjects who received continuously the same dose of CSL312 during both treatment periods, the two treatment periods will also be analyzed together. For C1-INH subjects having a dose change in Treatment Period 2, only data until the date and time of the dose change will be included in these summaries over both treatment periods for the safety analyses. For efficacy analyses, data until the date and time of the planned dose reduction will be included in these summaries over both treatment periods.

In Treatment Period 1, subjects with C1-INH HAE who are treated with placebo, [REDACTED] mg, [REDACTED] mg, or [REDACTED] mg CSL312 q4wk will be analyzed separately from subjects with C1-INH HAE who are treated with [REDACTED] mg CSL312 q2wk. In both treatment periods, subjects with FXII/PLG HAE will be analyzed separately from subjects with C1-INH HAE.

Summaries will be reported by treatment period and treatment in the following order:

- Treatment Period 1 FXII/PLG HAE: [REDACTED] mg CSL312 q4wk;
- Treatment Period 2 FXII/PLG HAE: [REDACTED] mg CSL312 q4wk;
- Treatment Period 1 & 2 FXII/PLG HAE: [REDACTED] mg CSL312 q4wk;
- Treatment Period 1 C1-INH HAE: placebo, [REDACTED] mg, [REDACTED] mg, and [REDACTED] mg CSL312 q4wk, Total Blinded Part and Total CSL312 (no totals will be populated for efficacy; for PK, [REDACTED] only Total CSL312);
- Treatment Period 1 C1-INH HAE: [REDACTED] mg CSL312 q2wk;
- Treatment Period 2 C1-INH HAE: [REDACTED] mg (initial and after down-titration), [REDACTED] mg in the Safety analysis], [REDACTED] mg CSL312 q4wk, and Total (no total will be populated for efficacy);
- Treatment Period 1 & 2 C1-INH HAE: [REDACTED] mg, [REDACTED] mg CSL312 q4wk, and Total (no total will be populated for efficacy) – only data included until dose change (Safety analysis) or planned dose reduction (Efficacy analysis).

The by-subject listings will include treatment period, treatment, subject number, and basic demographics (sex, age, body mass index [BMI]), and the information specific to that listing. The laboratory normal reference ranges will be provided and clinical laboratory test results outside the normal reference range will be flagged in the laboratory data listings.

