### 7.2 Treatment Descriptors

C1-INH HAE: Treatment Period 1 Blinded			
Placebo q4wk	●●● mg CSL312 q4wk	●●● mg CSL312 q4wk	●●● mg CSL312 q4wk

C1-INH HAE Treatment Period 1 Open-label
●●● mg CSL312 q2wk

C1-INH HAE: Treatment Period 2 Open-label		
CCI mg CSL312 q4wk	CCI mg CSL312 q4wk	CCI mg CSL312 q4wk

**CCI** mg CSL312 will be included only for the Safety analysis; **CCI** mg will include planned (for Efficacy and Safety analysis) and unplanned dose reduction for Safety analysis.

FXII/PLG HAE: Treatment Period 2 Open-label
CCI mg CSL312 q4wk

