**Treatment Period 1 and 2 (subjects who receive an IV loading dose of investigational product and who participate in Treatment Period 2):** From Week 1 Day 6 Visit of Treatment Period 1 (the date / time of the first SC administration of investigational product in Treatment Period 1) until the date / time of the Study Completion Visit or the date / time of planned dose reduction, whichever occurs first. The duration (days) of the efficacy evaluation period for Treatment Period 1 and 2 will be:

Study Completion Visit date and time or Date and time of planned dose reduction, whichever occurs first – Week 1 Day 6 Visit date and time + 1.

After planned dose reduction, data will not be included in the summary tables.

HAE attacks with start dates outside the above specified efficacy evaluation periods will not be included in the efficacy analysis but will only be listed:

- HAE attacks with a start date between the first and second administrations of the investigational product in Treatment Period 1,
- HAE attacks with a start date between Week 13 Day 85/91 and Week 21 Day 147,
- HAE attacks with start date between date of last treatment period visit and Follow-up.

**Safety Analysis Exposure:** The duration in days of the evaluation periods will be:

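### Efficacy time after a permitted dose increase in Treatment Period 2 stays under the assigned dose; this conflicts with the same-dose definition of the combined summary and can flatter the assigned dose if increases occur and help

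*SAP*

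**What the plan says.** Protocol 5.5 and SAP 4.3.2 plan no dose modification in Treatment Period 1 (TP1). In Treatment Period 2 (TP2), subjects on one named (redacted) dose who have three or more attacks in eight weeks "are eligible to have their CSL312 dose increased to" another level, at the investigator's discretion in consultation with the sponsor.

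For efficacy, SAP 10 uses planned treatment and states: "Unplanned dose reductions or dose increase to CCI mg CSL312 q4wk will not be considered for the Efficacy analysis". The TP2 efficacy windows in SAP 8.2.8 run from the Week 21 (Day 147) visit to study completion or, for one assigned dose, to the planned Amendment 2 reduction. None stops at an increase. SAP 7.2 adds of one TP2 dose column that "mg CSL312 will be included only for the Safety analysis".

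Protocol 10.3 has the two periods "analyzed together for subjects who are being continuously administered the same dose of CSL312 in both treatment periods"; SAP 10.1.2 and 10.2 use the same restriction. The cut-off for that combined summary is in SAP 7: "For efficacy analyses, data until the date and time of the planned dose reduction will be included in these summaries over both treatment periods". The safety version stops at any dose change (SAP 5 and 7).

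SAP 8.2.8 also makes one group of attacks listing-only: "HAE attacks with a start date between Week 13 Day 85/91 and Week 21 Day 147".

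**The concern.** The increase is open only to subjects who are doing badly on their assigned dose. If the raised dose helps them, their better later months are counted under the dose on which they qualified for the increase. A reader who takes a TP2 column as the result of a fixed dose would then see too low an attack rate and too many responders. The combined summary invites that reading, because it is defined by continuous treatment at one dose.

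This matters because Protocol 3.3.1 says: "The data from this study will be used to select dose(s) for a potential phase 3 study". The tables within reach are the TP2 and combined efficacy summaries and the TP2 between-dose responder comparison in SAP 10.2.1, which is cut only at the planned reduction.

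**Working it through.** **1. The plan's own figure.** The plan gives no number for this point. Its one numerical target is about 82% power in TP1, with 7 per arm and Poisson rates of 2.9 and 0.6 per month. SAP 4.5 adds: "Alpha is 2.5% for each of the 2 two-sided Mann-Whitney tests of" the two tested doses against placebo. A large-sample approximation for the Mann-Whitney test gives 81.97%. TP1 allows no dose change, so this calculation is unaffected.

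**2. Rules side by side.**

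| Summary | Label | Window closes at |
|---|---|---|
| TP2 efficacy | planned dose | completion or planned reduction |
| TP1+TP2 efficacy, same dose | planned dose | completion or planned reduction |
| TP1+TP2 safety, same dose | actual dose | any dose change |

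An increased subject has not received one dose continuously, so the definition read literally leaves the subject out. The cut-off rule and SAP 10 keep the subject in. Two programmers could produce different tables.

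**3. One illustrative subject (assumed course).** Three attacks in Days 147-203, an increase at Day 203, none afterwards, completion at Day 399.

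- Credited TP2 rate: 3 / 252 x 30.4375 = 0.36/month.
- Rate before the increase: 3 / 56 x 30.4375 = 1.63/month. The ratio is 56/252 = 0.22, or 78% lower.
- The extra day in the SAP's duration formula barely matters: 3/253 and 3/57 give 0.36 and 1.60.
- With an assumed run-in rate of 3/month, the reduction is 1 - 1.63/3 = 46% (non-responder) before the increase and 1 - 0.36/3 = 88% (responder) as credited. The switch needs a run-in rate below 2 x 1.63 = 3.26/month. At 4/month the subject responds either way (1 - 1.63/4 = 59%).
- Combined window from Day 6, with no other attacks: 3/394 x 30.4375 = 0.23/month as planned, and 3/198 x 30.4375 = 0.46/month if closed at the increase.

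**4. The early route.** Days 91-147 span 56 days, exactly the trigger period. If the three attacks fall there and the increase is at Day 147, the attacks are only listed and the whole TP2 window is spent on another dose. With no later attack, the credited rate is 0/month and the subject counts as attack-free in TP2.

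**5. Group level.** The documents give no effect of the raised dose, no between-subject spread and no share of subjects increased, so these are assumptions. The simulation used an assigned-dose rate of 0.6/month (the active rate in SAP 4.5), follow-up over Days 91-399, a switch at the next 28-day dose after three attacks within 56 days, and every triggered subject increased.

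| Spread between subjects | Rate ratio after increase | Mean credited rate | Change |
|---|---|---|---|
| none | 1.0 | 0.60 | 0% |
| none | 0.5 | 0.49 | -18% |
| none | 0.2 | 0.42 | -31% |
| gamma, shape 0.5 | 1.0 | 0.60 | 0% |
| gamma, shape 0.5 | 0.5 | 0.39 | -36% |
| gamma, shape 0.5 | 0.2 | 0.26 | -57% |

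Over assigned-dose rates of 0.3-1.2/month and ratios of 0.5-0.2, the change runs from -5% to -69%. If only half of the triggered subjects are increased (spread, ratio 0.5), it is -18%. At 0.6/month the median, which is the plan's primary summary, stays at 0.24 with spread and falls from 0.60 to 0.48 without.

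**6. The alternatives.** With spread at 0.6/month, closing at the increase gives 0.24 pooled, or 0.46-0.47 as a mean of subject rates, against 0.60 on a fixed dose. Without spread at 1.2/month, the mean of subject rates goes the other way: 1.59 against 1.20. Dropping increased subjects altogether gives 0.14 against 0.60.

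**The case against.** The strongest reply is that this is an openly declared rule and not a slip. The ITT definition (Protocol 10.2.2, SAP 6.2) analyses subjects as assigned, whatever they in fact received. That validly describes a policy of starting on a dose with an increase allowed. This stands for the TP2-alone tables.

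It does not cover the combined summary, whose own definition is one dose throughout. Nor is the SAP purely as-assigned: it moves time after the Amendment 2 reduction to the new dose, and it starts the TP2 window once steady state is assumed.

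Other parts of the reply also stand. The increase is discretionary. SAP 11.2 already tabulates dose changes, separating planned from unplanned, and lists date and level, though without linking them to efficacy. Doses are redacted, so whether the increase leads to the randomised comparator or to the safety-only level cannot be confirmed.

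A reader might infer that attack-free results are distorted generally. They are not: within TP2, a subject whose triggering attacks fall inside the window is already not attack-free, so only the Day 91-147 route has that effect.

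**Conclusion.** The point holds in a limited form. TP2 efficacy time after a permitted increase stays under the assigned dose, and in the combined summary this conflicts with the summary's definition and with the parallel safety rule. It can make the assigned dose look better if increases occur and help. The illustrative subject shows 0.36 against 1.63/month, and the simulated mean shifts by -5% to -69% for assumed rate ratios of 0.5-0.2. If nobody is increased or the increase does nothing, the effect is zero.

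A reader might go further and infer that the assigned dose's results are biased outright, or that the dose-response needed for phase 3 is hidden. The documents do not support either. They give neither the number increased nor the effect of an increase, and the randomised TP1 comparisons, including both confirmatory tests and the TP1 dose-versus-dose test, are untouched. The reach is the TP2 and combined descriptive summaries and the TP2 responder comparison. It is a modest, inexpensive correction.

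**What to change.** 1. In SAP 7, 8.2.8 and 10, reconcile the passages on the combined same-dose efficacy summary by closing its window at any dose change, as safety does.
2. Keep the TP2 table by assigned dose and label it *assigned dose, increase permitted*. Add a supplementary TP2 efficacy table by dose actually received, allowing in it the column that SAP 7.2 reserves for safety, with the number and timing of increases. Add a responder sensitivity analysis that counts increased subjects as non-responders on the assigned dose.

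The cost is SAP wording, one descriptive table and one sensitivity analysis; dose-change dates are already needed for safety. The downside is that closing at the increase depends on outcome and can move the rate in either direction. For a subject increased at Day 147 it leaves essentially no TP2 window on the assigned dose. Neither version should therefore stand alone. No change to the clinical dose-modification rule is proposed.

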## 10.1 Primary Efficacy: Analysis of Time-Normalized Number of HAE Attacks in Treatment Period 1 (Blinded Part)

The ITT population will be used for the primary analysis and the PP will be used as the secondary.

As outlined in Section 8.2.8, HAE attacks with a start date not falling into the efficacy evaluation period will not be included in the analyses of efficacy but will be presented in a listing only.

Subjects will enter HAE symptoms into their eDiary and the start and end date and time, the interference of HAE symptom(s) with daily activities, and location(s) of the HAE symptom(s). Investigator-reported HAE attacks will be based upon review of subject diaries, relevant interval medical history, and physician judgment. The investigator may ask clarifying questions to assist in his/her assessment of whether or not an HAE attack occurred. If an attack occurred, then the investigator will record an attack in the eCRF, the start/end date, the attack location(s), and the severity of the attack based on the most severe symptoms. For every visit, the Investigator will report all HAE attacks that have occurred in the interim since the last visit the subject attended.

For the analyses, a HAE attack is defined based on the HAE attacks reported by the investigator using the HAE attack eCRF.

In the primary analysis, only subjects with C1-INH HAE who receive q4wk SC dosing (after an IV loading dose) in a blinded manner will be included. The evaluation periods are defined in Section 8.2.8.

The time-normalized number of HAE attacks per month during Treatment Period 1 for a subject will be calculated as:

$$(\text{number of HAE attacks} / \text{length of subject's evaluation period in days}) * 30.4375$$

where the length of subject's evaluation period is defined in Section 8.2.8.

The time-normalized number of HAE attacks per month will be summarized descriptively including median (primary) and mean (secondary) with corresponding 95% CIs by blinded treatment (i.e., placebo, or bci mg, bci mg, or bci mg CSL312 q4wk).

To test for a difference in the primary efficacy endpoint between [b] mg CSL312 q4wk or [b] mg CSL312 q4wk and placebo q4wk, pairwise comparisons will be performed by testing the hypotheses using a two-sided Mann-Whitney test.

To account for multiple testing, the alpha level of 5% will be evenly split between the hypotheses tested. Therefore, the [b] mg CSL312 q4wk or [b] mg CSL312 q4wk CSL312 doses will each be evaluated against placebo q4wk at  $\alpha = 0.025$ :

$H_{01}: a_1 = 0$  versus  $H_{11}: a_1 \neq 0$

and

$H_{02}: a_2 = 0$  versus  $H_{12}: a_2 \neq 0$

In the above hypotheses, the term “ $a_1$ ” is the shift between the 2 distributions of [b] mg CSL312 q4wk and placebo q4wk and the term “ $a_2$ ” is the shift between the distributions of [b] mg CSL312 q4wk and placebo q4wk, respectively.

For the difference in the primary endpoint between the 2 treatments [b] mg and [b] mg CSL312 q4wk in Treatment Period 1, a comparison will be performed as an [b] using a two-sided Mann-Whitney test at  $\alpha = 0.05$ :

$H_{03}: a_3 = 0$  versus  $H_{13}: a_3 \neq 0$

where the term “ $a_3$ ” is the shift in the 2 distributions of the 2 CSL312 doses compared against each other.

There will be no testing of the [b] mg CSL312 q4wk dose against placebo q4wk. The time-normalized number of HAE attacks will be presented descriptively only.

A by-subject listing will be generated as specified in Section 7 and in addition showing the subject reported HAE symptoms, the HAE attack identifier as entered by the investigator with start and end date and time and duration (days), HAE attack location(s), and severity. HAE attacks with a start date falling into the efficacy evaluation period and HAE attacks treated with on-demand treatment for HAE attacks will be flagged. Details of the on-demand treatment will be provided in another by-subject listing. Derived efficacy variables such as number of HAE attacks and the time-normalized number of HAE attacks per month for each treatment period and for both treatment periods for subjects who received the same dose will be presented in another by-subject listing.

### 10.1.1 Sensitivity Analysis for Primary Efficacy: Missing Values for the Time-normalized Number of HAE Attacks in Treatment Period 1

To assess the impact of missing data for the primary efficacy variable a systematic approach will be applied. Imputation techniques based on MCMC methodology are considered inappropriate for this study with very small sample size.

For each treatment (i.e., placebo q4wk, [REDACTED] mg, or [REDACTED] mg CSL312 q4wk), a range of values for the number of time-normalized HAE attacks per month from 0 to 6 subdivided into 9 increments between two consecutive integer values will be generated. For the two comparisons of active treatment versus placebo all possible combinations from the subdivided ranges will be imputed to replace the missing values and the data will be analyzed using the Mann-Whitney test. Results will be classified into negative (i.e., placebo significantly better), neutral (i.e., no significant difference) and positive (i.e., active treatment significantly better) and depicted in a table and 2 graphs where the x-axis presents the subdivided range for placebo and the y-axis the subdivided range for the active treatment. The different outcomes will be distinguished by different symbols. This will only be applied to the ITT population.

